Protocol Number: NVGN-0084-201 Version: Amendment 4 IND Number: 112,608

Dose-Escalation Rules

Dose-escalation will occur in Stage 1:

The initial dose (Dose Level 0) for QD MTD determination in will be 60 mg. Dose levels will increase in 15 mg steps:

- The dose-escalation portion of the study (Stage 1) will use a "3 + 3" design to assess the safety, tolerability, and PK of GDC 0084 administered orally in 28-day cycles:
- Each dose cohort will initially enroll 3 patients. If none of these patients experiences a DLT within the DLT assessment period (Day 1 - 28), escalation will proceed to the next higher dose level by opening the next higher dose cohort with newly recruited patients;
- If 1 patient experiences a DLT, the cohort will be expanded until a second patient experiences a DLT or to a maximum of 6 patients. When a second patient has a DLT, the MTD is determined as 1 dose level below the current dose level; i.e. the highest dose level at which less than 1/3 of patients (e.g. 1 of 6) experiences a DLT will be declared the MTD.
- If 2 or more patients experience a DLT at Dose Level 0, the MTD will be declared at 45 mg, which was the MTD established in the previous phase I study in patients with advanced glioma with a QD dosing schedule.

On the basis of the review of real-time safety data and available preliminary PK data from this study with GDC-0084, dose-escalation may be halted or modified by the sponsor as deemed appropriate.

Decisions regarding dose-escalation and selection will be made by a CRC including the medical monitor, recruiting Investigators, sponsor representative and any other relevant and necessary expert on as needs basis, according to the CRC charter.

Definition of Dose Limiting Toxicity

All AEs, including DLTs, will be reported, with severity assessed according to National Cancer Institute (NCI) Common Terminology Criteria for Adverse Events (CTCAE), version 4.03. In case a patient experiences one of the below, study participation will be terminated for this patient and the EoT visit should be performed.

For dose-escalation purposes, DLT assessments will be performed by the sponsor in consultation with the Investigators during the CRC meetings.

A DLT is defined as any one of the following toxicities occurring within the DLT assessment window (Cycle 1, Days 1 - 28) and assessed by the Investigator to be probably or possibly related to GDC-0084:

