- Mucositis/stomatitis Grade 3 not responding to standard-of-care therapy or Grade 4. Sites should consider using an alcohol-free dexamethasone 0.5 mg per 5mL oral solution (elixir) if such symptoms eventuate. Patients may be instructed to use 10ml oral solution swished for up to two minutes and then spit, up to four times daily (Rugo et al. 2017).
- Decrease in left ventricular ejection fraction (LVEF) to ≤ 45%;
- Increase of QTc to ≥ 500 msec or by 60 msec:
- Pneumonitis Grade ≥ 2.

After determination of the MTD, patients continue to receive their protocol assigned dose levels of GDC-0084 until progression of their disease or an unacceptable toxicity, whichever occurs first.

Patients who experience disease progression or an unacceptable toxicity at any time during the study, or, in their opinion or the opinion of the Investigator, are not benefiting from GDC-0084, will be discontinued from study treatment. Under certain circumstances in which an AE (or DLT) is reversible and the risk/benefit assessment suggests a reasonable rationale for continued administration of study drug, patients may continue with agreement from the Investigator and the medical monitor. This may include dose reduction and change of treatment schedule. An End of Treatment visit will be performed approximately 28 days after the last dose of GDC-0084.

3.7.2 Stage 2

Stage 2 of the study will be a two-arm, randomized, open-label expansion cohort to further characterize safety, tolerability and PK of GDC-0084 when administered QD in 28-day cycles, and to explore the effect of food on the PK of GDC-0084, as well as to provide a preliminary assessment of single-agent activity of GDC-0084 in patients with GBM.

The expansion will start with a screening period, followed by treatment and follow-up periods. It will be initiated with recruitment of new patients as soon as the MTD for QD dosing has been determined.

Approximately 20 patients will be enrolled in the expansion cohort according to the defined study eligibility criteria, to perform the comparison of safety and clinical activity. On Days 1 and C2D1, 10 patients will receive GDC-0084 in a fed state, while the remaining 10 patients will receive GDC-0084 in a fasted state. Patients will be allocated to either fed or fasted arms via a central randomization mechanism.

Patients enrolled in Stage 2 may continue the study at the dose allocated until disease progression or unacceptable toxicity.

Version: Amendment 4 Date: 31 Mar 2020

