4.2 Eligibility Criteria

4.2.1 **Inclusion Criteria**

Patients must meet all the following inclusion criteria to be eligible for enrollment into the study:

- 1) Signed informed consent approved by the Institutional Review Board (IRB). Patients must sign an authorization for the release of their protected health information;
- 2) Age ≥ 18 years;
- 3) Life expectancy > 12 weeks;
- 4) Present with histologically confirmed intracranial (supratentorial) unmethylated MGMT promotor status GBM (WHO Grade IV astrocytoma) with an MGMT status that has been confirmed by validated PCR or validated alternative genomic analysis;
- 5) Have undergone maximal or subtotal surgical resection of their tumor and within 6 weeks of surgery commenced radiation and then received at least 75% of planned treatment with XRT/TMZ or XRT only (if clinically indicated), which consists of XRT by external beam to a partial brain field in daily fractions of 2.0 Gray (Gy), to a planned total dose to the tumor of 60.0 Gy, in conjunction with TMZ oral QD 75 mg/m² in accordance with the Stupp regimen;
- 6) Karnofsky Performance Status (KPS) ≥ 70;
- 7) Cranial magnetic resonance imaging (MRI) must have been performed within 14 days prior to or on the day of the Enrollment/Week 1 Visit;
- 8) Stable or decreasing corticosteroid dose within 7 days prior to the first dose;
- 9) Adequate bone marrow/hematological function within 14 days prior to Day 1:
 - White blood cell count (WBC) > 3,000/µL, absolute neutrophil count > 1,500/mm³;
 - Platelet count of > 100,000/mm³;
 - Hemoglobin > 10 mg/dL;
 - Eligibility level for hemoglobin may be reached by transfusion;
- 10) Adequate liver function within 14 days prior to Day 1:
 - Total bilirubin ≤ 1.5 x ULN;
 - AST and ALT ≤ 2.5 x ULN;
- 11) Adequate renal function within 14 days prior to Enrollment/Week 1 Visit:
 - Creatinine ≤ 1.5 mg/dL;
 - Urine dipstick for proteinuria < 2+. Patients discovered to have ≥ 2+ proteinuria on dipstick urinalysis should undergo a 24-hour urine collection and must demonstrate ≤ 1.0 g of protein in 24 hours: OR
 - Urine protein/creatinine ratio ≤ 1.0;
- 12) International normalized ratio (INR) or prothrombin time (PT) (secs) and activated partial thromboplastin time (aPTT) within 7 days prior to Enrollment:
 - ≤1.5 x ULN (except for patients receiving anticoagulation therapy) in the absence of therapeutic intent to anti-coagulate the patient;

Version: Amendment 4 Date: 31 Mar 2020

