4.2.2 Exclusion Criteria

Patients presenting with any of the following will not be included in the study:

- 1) Previous radiotherapy to the brain or cytotoxic drug therapy (including Gliadel® wafers) in addition to the required postoperative radiation plus TMZ, non-cytotoxic drug therapy, or experimental drug therapy directed against the brain tumor prior to this regimen, will be excluded. Patients may have received or be receiving corticosteroids, analgesics, and other drugs to treat symptoms or prevent complications but the dose must be stable at treatment start. NOTE: 5 aminolevulinic acid-mediated photodynamic therapy administered prior to surgery to aid in optimal surgical resection is not considered a chemotherapy agent;
- 2) Any prior, or anticipated, concomitant treatment involving a medical device (such as Optune®) applying tumor treating fields (TTF). Prior short-course Optune® monotherapy (i.e. without concurrent TMZ or other chemoRx) may be allowed with approval from the Medical Monitor
- 3) QT interval time of ≥ 470 msec;
- 4) Undetermined/indeterminate MGMT status;
- 5) Diabetic patients and/or ongoing use of insulin therapy; clinically confirmed prediabetic patients;
- Use of any strong CYP3A4 inducing or inhibiting agents within 14 days of first dose of GDC-0084;
- 7) Significant medical illnesses that in the Investigator's opinion cannot be adequately controlled or would compromise the patient's ability to tolerate this therapy;
- 8) Women who are pregnant (determined by serum beta chorion-gonadotropin) or who are lactating. NOTE: Serum pregnancy test to be assessed within 7 days prior to first dose;
- 9) Any disease likely to obscure toxicity;
- 10) Diagnosed with infratentorial GBM;
- 11) Diagnosed with tumor outside of brain;
- 12) Diagnosed with gliomatosis cerebri;
- 13) Evidence of recent hemorrhage on postoperative MRI of the brain. However, patients with clinically asymptomatic presence of hemosiderin, resolving hemorrhagic changes related to surgery, and presence of punctate hemorrhage in the tumor are permitted entry into the study;
- 14) Male and female patients of childbearing potential unwilling or unable to use effective means of contraception (oral contraceptives, intrauterine contraceptive device, barrier method of contraception in conjunction with spermicidal jelly) throughout the study and for at least 28 days after the last dose of assigned treatment;

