Prior to the scheduled FDG injection, patients should fast for at least 4 hours (preferably 6 hours). The blood glucose level should be determined at the time of the FDG-PET scan. Use of anti-hyperglycemic medications, including insulin, immediately prior to the FDG-PET scan is not permitted, as these agents will impact FDG uptake and compromise the interpretability of the FDG-PET scan. Specifically, no short-acting insulin should be administered within 4 hours prior to FDG administration.

Median and mean FDG-PET standard uptake value within the contrast enhancing, measurable target lesion(s), contralateral normal-appearing cortical tissue, and contralateral normal-appearing white matter will be quantified.

4.6.4 **Cardiac Assessment**

Cardiac assessment will be performed by the Investigator and be based on assessment of medical history, physical examination, 12-lead ECG results (including QTc) and evaluation of LVEF by echocardiography (ECHO) or multi-gated scan (MUGA) as well as, as clinically indicated, measurement of troponin T and B-type natriuretic peptide as potential biomarkers of early

Version: Amendment 4 Date: 31 Mar 2020

cardiotoxicity. Cardiology consult may be sought by the Investigator if required to confirm suitability for inclusion in the study.

Protocol Number: NVGN-0084-201

IND Number: 112.608

Except for baseline ECGs at screening, ECGs should be conducted approximately 2 hours post-dose, to coincide with the approximate timing of T_{max} determined in a prior clinical study.

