4.10.6 Potential Cardiac Effects

One patient receiving 15 mg GDC-0084 QD in Cohort 4 of study GO28070 experienced an AE of Grade 2 bradycardia and Grade 3 myocardial ischemia, and 1 patient receiving 30 mg GDC 0084 QD in Cohort 6 experienced an event of Grade 2 myocardial infarction. Both patients developed asymptomatic cardiac ischemia accompanied by troponin elevations and ECG T-wave inversions. One subject dosed at 30 mg GDC-0084 had a QTcF value marginally greater than 450 msec at 24 h after dosing, and five subjects had QTcF increases of > 30 msec above baseline on at least one occasion, but no QTcF increases > 60 msec were recorded.

Analysis of the relationship between GDC-0084 plasma concentrations and QTcF showed a slight positive trend for absolute QTcF and QTcF change from baseline. Based on this limited sample size. GDC-0084 has the potential to prolong the QTc interval. Patients with QTc interval > 470 msec will be excluded from this study and a specific, detailed QT and overall cardiac risk mitigation plan will be observed for phase 2.

Patients with significant cardiac history (e.g., myocardial infarction or symptomatic bradycardia, active congestive heart failure, and angina pectoris) should be excluded from study participation. During the study, patients should be instructed to contact their treating physician if they experience dizziness, light-headedness, fainting, sensations of heart palpitations, or slow or irregular pulse. Electrocardiograms should be closely monitored. Cardiac enzymes may be measured if deemed necessary.

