Values and changes from baseline (last value obtained prior to first dose) in clinical laboratory results will be summarized by visit. Clinical laboratory values will be graded according to the NCI CTCAE 4.03, for applicable tests. Shifts in CTC grades from baseline grade will be summarized. The number and percentage of patients with treatment-emergent Grade 3/4 clinical laboratory abnormalities will also be presented. The number and percentage of patients with abnormally high glucose values (hyperglycemia) or abnormally low platelet values (thrombocytopenia) will be summarized overall and by CTC grade (since these are DLT criteria).

KPS data will be summarized categorically (number and percentage of patients with each score at each visit).

Values and changes from baseline in vital signs will be summarized by visit.

Values and changes from baseline in ECG, parameters will be summarized by visit. The number and percentage of patients with an increase of QTc to ≥ 500 msec or a change from baseline of at least 60 msec will be presented overall and by visit. The number and percentage of patients with ECG abnormalities at each visit will also be presented.

Values and changes from baseline in LVEF will be summarized by visit. The number and percentage of patients with a drop in LVEF to ≤ 45% will be presented. Troponin T and B-type natriuretic peptide values will be listed.

Changes in corticosteroid use will be summarized. Further details on corticosteroid use will be defined in the SAP.

Concomitant medications are defined as any medications taken on/after the first study drug dose (including those started prior to first dose and ongoing at time of first dose) and within 28 days after

Version: Amendment 4 Date: 31 Mar 2020

Date. 31 Wai 2020

the last dose date. Concomitant medication use will be summarized. Any medications started and stopped prior to first dose or started after last dose + 28 days will be listed but not summarized.

Protocol Number: NVGN-0084-201

IND Number: 112.608

Treatment exposure will be summarized. Patient diaries will be used to assess compliance.

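### Exclusion 3 limits uncorrected QT while section 4.10.6 limits QTc, so the listed ECG criterion is not on the scale of the QTc-based DLT rule

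*Combined protocol and SAP*

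**What the plan says.** Four places in the protocol set a QT or QTc threshold.

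- Section 4.2.2, exclusion 3: "QT interval time of ≥ 470 msec". This is the only ECG limit in the eligibility list.
- Section 4.10.6, within the supportive-care guidelines: "Patients with QTc interval > 470 msec will be excluded from this study".
- Section 3.7.1, DLT definition: "Increase of QTc to ≥ 500 msec or by 60 msec". The event must fall in Days 1 to 28 of Cycle 1 and be "assessed by the Investigator to be probably or possibly related to GDC-0084".
- Section 6.3.5, safety analysis: a count of patients with an "increase of QTc to ≥ 500 msec or a change from baseline of at least 60 msec".

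Section 4.3 makes enrollment depend on checking the inclusion and exclusion criteria on an eligibility worksheet. Section 4.6.4 already makes QTc part of the 12-lead ECG assessment. Section 4.10.6 reports the earlier study's data as QTcF, but no correction is named for eligibility or for the DLT in this study.

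On corticosteroids, inclusion 8 in 4.2.1 requires "Stable or decreasing corticosteroid dose within 7 days prior to the first dose". Exclusion 1 in 4.2.2 lets patients receive corticosteroids "but the dose must be stable at treatment start".

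**The concern.** An eligibility limit on a safety measurement should be on the same scale as the toxicity rule that later uses that measurement. Here the listed criterion is on raw QT and the toxicity rule is on QTc. The two agree at 60 bpm and separate as heart rate moves away from it. A worksheet built from the list could therefore admit patients whom 4.10.6 says are excluded, and turn away others whom 4.10.6 would allow.

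The stake is the reading of the primary endpoint. In the 3+3 design one DLT expands a cohort, and a second sets the MTD one dose level lower. With 3 to 6 patients per level, one QTc event that reflects a high starting value rather than a drug effect can alter the dose decision. Section 4.10.6 itself says that the drug may prolong QTc, so this DLT limb may well be used. By Table 1, note f, every ECG except the screening one is taken about two hours after dosing, so no second pre-dose ECG is scheduled that would show the problem.

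The corticosteroid wording is a smaller matter of the same kind: two entry criteria that do not fit together for one group of patients.

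**Working it through.** **Inputs.** From the protocol: QT ≥ 470 msec (4.2.2), QTc > 470 msec (4.10.6), and QTc ≥ 500 msec or a 60 msec increase (3.7.1 and 6.3.5). Assumed, because the documents give neither: heart rates (HR) of 50 to 100 bpm, and four common correction formulas. The plan states no derived figure to reproduce.

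**Formulas.**

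- Bazett: QTc = QT / (60/HR)^(1/2)
- Fridericia: QTc = QT / (60/HR)^(1/3)
- Framingham: QTc = QT + 154 × (1 − 60/HR)
- Hodges: QTc = QT + 1.75 × (HR − 60)

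**Can a QT that passes exclusion 3 give a high QTc?** Take QT = 469 msec at 80 bpm, where 60/HR = 0.75. The last two columns give the approximate heart rate at which QTc reaches 500 msec.

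| Formula | QTc for QT 469 at 80 bpm | HR for QTc 500, QT 469 | HR for QTc 500, QT 450 |
|---|---|---|---|
| Bazett | 469 / 0.75^(1/2) = 542 | 68 | 74 |
| Fridericia | 469 / 0.75^(1/3) = 516 | 73 | 82 |
| Framingham | 469 + 154 × 0.25 = 508 | 75 | 89 |
| Hodges | 469 + 1.75 × 20 = 504 | 78 | 89 |

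An admissible QT can therefore correspond to a QTc of 500 msec or more under every formula. The heart rate needed depends on the formula by about 10 bpm at QT 469 and 15 bpm at QT 450. Away from the extreme value, Fridericia gives 460 / 0.75^(1/3) = 506 msec at 80 bpm. It gives 400 / 0.6^(1/3) = 474 msec at 100 bpm, which is above the 4.10.6 limit but below 500.

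**Where does the effect stop?** At 60 bpm all four formulas return QTc = QT, and below 60 bpm they return a smaller value. So at 60 bpm or below, no QT under 470 msec gives a QTc of 470 msec or more.

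**The reverse direction.** QT = 480 msec at 50 bpm (60/HR = 1.2) is excluded by 4.2.2(3). Its QTc is:

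- Bazett: 480 / 1.2^(1/2) = 438
- Fridericia: 480 / 1.2^(1/3) = 452
- Framingham: 480 + 154 × (−0.2) = 449
- Hodges: 480 + 1.75 × (−10) = 462.5

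All are within the 4.10.6 limit.

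**The boundary.** At 60 bpm a value of exactly 470 msec is excluded by 4.2.2(3) and allowed by 4.10.6.

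**Margin to the DLT limb.** Under 4.10.6 the highest QTc at entry is 470 msec, which leaves 500 − 470 = 30 msec. For any baseline above 500 − 60 = 440 msec, the 500 msec limb is reached before the 60 msec limb, so the margin is 500 minus the baseline. On exclusion 3 alone that margin has no lower bound above zero. A patient at QTc 495 msec needs a rise of only 5 msec.

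**Corticosteroids.** Inclusion 8 covers the 7 days before first dose; exclusion 1 covers the start of treatment. A taper completed before Day 1 satisfies both. A dose still falling at first dose satisfies inclusion 8 and fails exclusion 1.

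**The case against.** The strongest reply is that the two exclusions are cumulative. A patient with a QTc of 506 msec is barred by 4.10.6 whatever the list says. Section 4.10.6 also refers to a QT and cardiac risk mitigation plan that is not in the documents. Section 4.6.4 provides QTc and allows a cardiology opinion on suitability, and exclusions 7 and 16 leave room for the investigator's judgement. This stands against one tempting inference, that the plan admits patients whose QTc is already at the DLT threshold. Read as a whole, it does not. What the reply leaves open is how the rule is applied. Section 4.3 ties enrollment to the listed criteria, and the QTc limit is not among them. The judgement-based exclusions set no QTc value.

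A second inference is that such a patient would count as a DLT with no drug effect at all. The text does not support that either. The rule needs an increase to 500 msec or more, judged at least possibly related, with the DLT assessment made at the cohort review meetings. An unchanged baseline value does not meet it. What remains is a patient just under 500 msec, for whom a small fluctuation judged possibly related would qualify, and a patient already at 500 msec, for whom that limb cannot be interpreted.

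Third, the heart rates are assumptions, and the documents give no QT distribution, so nobody can say how many patients are affected. That is right. Finally, section 6.3 leaves technical detail to a separate SAP, so the lack of a formula in 6.3.5 does not show that the analysis will have none. The gap is established for eligibility and the DLT only. The synopsis exclusion list is cut off in the supplied text and could not be compared.

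**Conclusion.** The point holds as an unreconciled conflict between two entry rules. Sections 4.2.2(3) and 4.10.6 differ in the interval and in the boundary sign, and the listed rule is not on the scale of the DLT criterion. The discrepancy can reach tens of msec: about 35 to 73 msec for a QT of 469 msec at an assumed 80 bpm (504 − 469 to 542 − 469), depending on the formula. It is nil at 60 bpm and runs the other way below that. These figures rest on assumed heart rates and formulas; the number of patients affected cannot be estimated.

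The consequence is conditional. If the list alone is applied, the margin of at least 30 msec implied by 4.10.6 can shrink or vanish, which weakens the QTc limb of the DLT definition.

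On corticosteroids, a reader might infer that the criteria contradict each other for anyone being tapered. They do so only for a patient still tapering at first dose. Both matters should be corrected; neither invalidates the design.

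**What to change.** Reconcile 4.2.2(3) and 4.10.6 to one interval, one boundary sign and one named correction formula, placed in the eligibility list that sites check. Use the same quantity and formula in the DLT definition in 3.7.1 and the summary in 6.3.5, and confirm that the synopsis matches. State how the 500 msec limb is read for a patient whose baseline is close to or at that value. Reconcile inclusion 8 with exclusion 1 so that the status of a patient still tapering at first dose is clear. The clinical values and the choice of rule are for the sponsor.

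The cost is wording in a protocol amendment and an edit to the eligibility worksheet. No new measurement is needed, because QTc is already part of the cardiac assessment.

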4.3 Enrollment Procedure

The Investigator will enroll the individual patients into the study. It is the Investigators responsibility that enrollment will only occur after all inclusion and exclusion criteria have been checked and eligibility of the patient is verified using a patient eligibility worksheet. This includes the collection of all necessary assessment results per the Schedule of Assessments (see Section 0).

